#### **12.3.3.1 Analysis of Primary Endpoint**

The primary efficacy endpoint is the **absolute change in CFQ-R respiratory domain score from baseline through Week 24**. The analysis of this endpoint will be performed using a mixed-effects model for repeated measures (MMRM) with absolute change from baseline in CFQ-R respiratory domain score at each post-baseline visit as the dependent variable. The model will include treatment group, visit, and treatment-by-visit interaction as fixed effects, and will be adjusted for selected covariates as appropriate. Details will be described in the SAP. The model will be estimated using restricted maximum likelihood. Denominator degrees of freedom for the F test for fixed effects will be estimated using the Kenward-Roger approximation. An unstructured covariance structure will be used to model the within-subject errors. If the model

estimation does not converge, a compound symmetry covariance structure will be used instead. Conditional on the observed data and covariates, missing data will be assumed to be missing at random; consequently, no imputation of missing data will be performed.

The primary result obtained from the model will be the estimated treatment difference through Week 24 (defined as the average of Weeks 4, 8, 16, 24). The least squares (LS) mean estimate with a 2-sided 95% CI and a 2-sided  $P$  value will be provided. The treatment difference at each post-baseline visit, obtained from the model, will also be provided.

Additional [REDACTED] or subgroup analyses if appropriate will be described in the SAP.

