4 INTRODUCTION

This statistical analysis plan (SAP) is based on the most recent approved clinical study protocol (CSP), the most recent approved electronic case report form (eCRF), and the most recent approved eCRF completion guidelines.

This SAP (Methods) documents the planned statistical analyses of efficacy and safety endpoints defined in the VX18-445-109 study protocol. It also documents analyses for additional efficacy and safety variables not specified in the protocol, which will provide supportive information for the scientific understanding of the drug entity.

The Vertex Biometrics Department will perform the statistical analysis of efficacy and safety data; SAS (Version 9.4 or higher) will be used to generate all statistical outputs (tables, figures, listings, and datasets). The SAP will be finalized and approved prior to the clinical database lock and treatment unblinding for the study. Any revisions to the approved SAP will be documented and approved in a SAP amendment prior to the clinical database lock and treatment unblinding. Any changes made to the SAP (Methods) after the clinical database lock has occurred will be documented in the clinical study report for this study.

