7.2 Sample Size and Power

The primary efficacy endpoint is the absolute change in CFQ-R respiratory domain score from baseline through Week 24. The primary null hypothesis to be tested is that the mean absolute change in CFQ-R respiratory domain score from baseline is the same for the 2 treatment groups, ELX/TEZ/IVA and TEZ/IVA. The null hypothesis will be tested at a 2-sided significance level of 0.05.

Assuming a within-group SD of 18 and a treatment difference of 10 between ELX/TEZ/IVA and TEZ/IVA, a sample size of 71 subjects completing the Treatment Period in each group for a total of 142 subjects will have approximately 90% power for the CFQ-R respiratory domain score hypothesis testing, based on a 2-sample *t*-test at a significance level of 0.05 (2-sided). Assuming a 10% dropout rate, approximately 158 subjects will be enrolled.

The key secondary endpoint is the absolute change in ppFEV₁ from baseline through Week 24. Assuming a within-group SD of 7 percentage points and a treatment difference of 5 between ELX/TEZ/IVA and TEZ/IVA, a sample size of 71 subjects completing the Treatment Period in each group for a total of 142 subjects will have approximately 98% power for the ppFEV₁ hypothesis testing, based on a 2-sample *t*-test at a significant level of 0.05 (2-sided).

All power calculations were based on EAST software Version 6.4.

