7.3 Randomization

Randomization will be stratified by ppFEV₁ determined during the TEZ/IVA Run-in Period (Day -14 assessment; <70 versus ≥70), age at the Screening Visit (<18 versus ≥18 years of age), and whether the subject is receiving CFTR modulator treatment at the Screening Visit (yes versus no). If the Day -14 ppFEV₁ value is not valid or not available, the most recent available ppFEV₁ value will be used for stratification.

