9.2.2 Demographics and Baseline Characteristics

Demographics and baseline characteristics will be summarized based on the FAS, and presented by treatment group and overall.

Demographic data will include the following:

- Age at baseline (in years)
- Sex (female and male)
- Ethnicity (Hispanic or Latino, not Hispanic or Latino, and not collected per local regulations)
- Race (White, Black or African American, Asian, American Indian or Alaska Native, Native Hawaiian or Other Pacific Islander, Other, and not collected per local regulations)
- Country

Baseline characteristics will include the following:

- Weight (kg)
- Height (cm)
- BMI (kg/m²)

Stratification categories will include the following:

- Age at Screening Visit (<18, ≥18 years)
- ppFEV₁ at Day -14 (<70, ≥70)
- CFTR modulator use at the Screening Visit (Yes, No)

Disease characteristics will include the following:

- CFQ-R respiratory domain score at baseline (continuous)
- ppFEV₁ at baseline (<40, ≥ 40 to <70, ≥70 to ≤90, and >90)
- ppFEV₁ at baseline (continuous)
- Sweat chloride at baseline (continuous)
- Prior use of dornase alfa before the first dose of study drug in the Treatment Period (Yes, No)
- Prior use of azithromycin before the first dose of study drug in the Treatment Period (Yes, No)
- Prior use of inhaled antibiotic before the first dose of study drug in the Treatment Period (Yes, No)
- Prior use of bronchodilator before the first dose of study drug in the Treatment Period (Yes, No)
- Prior use of inhaled bronchodilator before the first dose of study drug in the Treatment Period (Yes, No)
- Prior use of inhaled hypertonic saline before the first dose of study drug in the Treatment Period (Yes, No)

- Prior use of inhaled corticosteroids before the first dose of study drug in the Treatment Period (Yes, No)
- Infection with *Pseudomonas aeruginosa* within 2 years prior to screening (Positive, Negative)

In addition, data listings will also be provided for:

- Informed consent;
- Inclusion/Exclusion criteria violation for subjects with any such violations.

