9.3.1.2 Primary Analysis

The primary analysis will be performed using a mixed-effects model for repeated measures (MMRM) with the absolute change from baseline at each post-baseline visit as the dependent variable. The model will include treatment group, visit, and treatment-by-visit interaction as fixed effects, with continuous baseline ppFEV₁, age at Screening (<18 versus ≥18 years of age), and CFTR modulator use at Screening (yes versus no) as covariates. The model will be estimated using restricted maximum likelihood. Denominator degrees of freedom for the *F*-test for fixed

effects will be estimated using the Kenward-Roger approximation². An unstructured covariance structure will be used to model the within-subject errors. If the model estimation does not converge, a compound symmetry covariance structure will be used instead. Conditional on the observed data and covariates, missing data will be assumed to be missing at random; no additional imputation of missing data will be performed.

The primary result obtained from the model will be the estimated treatment difference through Week 24 (defined as the average of Weeks 4, 8, 16, 24). The least squares (LS) mean estimate with a 2-sided 95% CI and a 2-sided P value will be provided. The treatment difference at each post-baseline visit, obtained from the model, will also be provided.

The LS mean (with SE) obtained from the MMRM analysis at each post-baseline visit up to Week 24 will be plotted by treatment group. In addition, the post-baseline raw values and the absolute change from baseline at each post-baseline visit up to Week 24 will be summarized descriptively (n, mean, SD, median, minimum, and maximum).

The primary analysis will include all available CFQ-R RD data obtained at clinic and at home. An additional analysis using data before the outbreak of COVID-19 (defined as March 2, 2020) may be performed, if the CFQ-R RD data before COVID-19 are inconsistent with CFQ-R data during COVID-19. In addition, similar additional analysis using the CFQ-R RD data obtained at clinic only may be performed, if the CFQ-R RD data obtained at home due to COVID-19 are inconsistent with the CFQ-R RD data obtained at clinic. Such additional analysis results should be interpreted with caution due to reduced sample size.

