9.3.1.3 Subgroup Analysis

Subgroup analyses of the primary efficacy endpoint will be performed using a model similar to that of the primary analysis for each of the following subgroups:

- Age at Screening (<18, ≥18 years)
- ppFEV₁ at Baseline (< 70, ≥ 70)
- CFTR modulator use at Screening (yes, no)
- Sex (male, female)

The MMRM used for the primary analysis will be used for the subgroup analysis, where the same model will be applied to each category of the subgroup. For the subgroup analysis based on age, the covariate of age at screening (<18 versus ≥18 years) from the MMRM will be removed. For the subgroup analysis based on CFTR modulator use at Screening, the covariate of CFTR modulator use at Screening (yes, no) from the MMRM will be removed. The LS means with 2-sided 95% confidence intervals will be provided. Furthermore, the estimated treatment difference through Week 24 in different categories within a subgroup will also be presented in a forest plot. Note that the results from the subgroup analysis should be interpreted with caution in the cases where sample sizes are small.

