9.3.3.2 Analysis Method

Analysis of absolute change from baseline through Week 24 in sweat chloride will be based on an MMRM that is same as the primary analysis of the primary efficacy variable. The primary result obtained from the model will be the estimated treatment difference through Week 24 (defined as the average of Weeks 4, 8, 24). The LS mean estimate with a 2-sided 95% CI and a 2-sided nominal *P* value will be provided. The treatment difference at each post-baseline visit, obtained from the model, will also be provided.

The LS mean (SE) at each visit will also be plotted by treatment group. In addition, the post-baseline raw values and the absolute change from baseline at each post-baseline visit up to Week 24 will be summarized descriptively (n, mean, SD, median, minimum, and maximum).

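### The primary CFQ-R MMRM is valid and meets its stated power, but it leaves out baseline CFQ-R and so gives up precision that would cost nothing to keep; the SwCl model, read literally, leaves out baseline SwCl

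*SAP*

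**What the plan says.** The dependent variable in SAP 9.3.1.2 is the absolute change in CFQ-R respiratory domain score at each post-baseline visit. The fixed effects are treatment, visit and their interaction, "with continuous baseline ppFEV₁, age at Screening (<18 versus ≥18 years of age), and CFTR modulator use at Screening (yes versus no) as covariates". The primary estimate is the treatment difference averaged over Weeks 4, 8, 16 and 24.

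The three covariates follow the stratification factors. SAP 7.3 begins "Randomization will be stratified by ppFEV₁ determined during the TEZ/IVA Run-in Period" and adds age group and modulator use at screening. The model takes ppFEV1 as continuous, at baseline. Protocol 12.3.3.1 says only that the model is "adjusted for selected covariates as appropriate" and leaves the details to the SAP. Neither document adds baseline CFQ-R elsewhere.

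The variable exists. Protocol Table 3-2 schedules the questionnaire on Day 1, and SAP 9.2.2 summarises it among the disease characteristics ("CFQ-R respiratory domain score at baseline (continuous").

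Other models inherit the list. For subgroups, SAP 9.3.1.3 uses the primary MMRM, "where the same model will be applied to each category of the subgroup". For sweat chloride, SAP 9.3.3.2 specifies an "MMRM that is same as the primary analysis of the primary efficacy variable". SAP 9.3.2.2 uses the same model for ppFEV1, so the key secondary endpoint is adjusted for its own baseline while the primary endpoint is not.

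**The concern.** A change score subtracts the baseline with a coefficient of exactly 1. If the regression of follow-up on baseline has a slope below 1, the change is negatively correlated with baseline. That part of the variance stays in the residual unless baseline is a covariate. Baseline ppFEV1 is a different measurement and does not stand in for it.

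At stake is the width of the primary confidence interval. The realised estimate also moves with any chance imbalance in baseline CFQ-R between arms. That movement is the same loss of precision seen conditionally, not a second problem. The subgroup estimates, which the SAP itself says need caution where samples are small, carry the same loss.

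A smaller point is that the missing-at-random assumption in SAP 9.3.1.2 is conditional on the observed data and covariates. If dropout depends on baseline CFQ-R, having it in the model makes that assumption easier to defend.

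**Working it through.** **Inputs from the documents.** SAP 7.2: "Assuming a within-group SD of 18 and a treatment difference of 10 between ELX/TEZ/IVA and TEZ/IVA", 71 completers per arm, two-sided alpha 0.05, two-sample t-test. I take 18 as the SD of the averaged change in the planned model.

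**Inputs assumed.** Correlation rho = 0.5 to 0.8 between baseline and each follow-up visit, and equal variances at baseline and follow-up. The documents give neither.

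**The plan's own figure.** SE = 18 × sqrt(2/71) = 3.02. Noncentral-t power for a difference of 10 with 140 df is 90.8%, which agrees with the stated figure of about 90%. The 95% half-width is 1.977 × 3.02 = 5.97 points.

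**Variance ratio.** Let B be baseline and A the mean of the four follow-up visits, with common variance σ² at each visit. Adding B as a covariate changes the residual variance from Var(A − B) to Var(A | B).

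- *All visits exchangeable* (visit-to-visit correlation also rho): Var(A) = σ²(1+3rho)/4, Var(A | B) = σ²(1−rho)(1+4rho)/4 and Var(A − B) = 5σ²(1−rho)/4. The ratio is (1+4rho)/5.
- *Follow-up visits perfectly correlated with each other*: Var(A | B) = σ²(1−rho²) and Var(A − B) = 2σ²(1−rho). The ratio is (1+rho)/2. Averaging over visits then removes no noise, so the gain is smaller.

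Power and half-width use SD = 18 × sqrt(ratio). Equivalent completers are 71 × ratio.

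| Form | rho | Variance cut | Power | Half-width | Equivalent completers per arm |
|---|---|---|---|---|---|
| Exchangeable | 0.5 | 40% | 98.9% | 4.63 | 42.6 |
| | 0.6 | 32% | 97.9% | 4.93 | 48.3 |
| | 0.7 | 24% | 96.5% | 5.21 | 54.0 |
| | 0.8 | 16% | 94.8% | 5.47 | 59.6 |
| Perfectly correlated | 0.5 | 25% | 96.7% | 5.17 | 53.2 |
| | 0.6 | 20% | 95.7% | 5.34 | 56.8 |
| | 0.7 | 15% | 94.6% | 5.51 | 60.3 |
| | 0.8 | 10% | 93.4% | 5.67 | 63.9 |

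**Chance imbalance.** Without the term, a baseline imbalance of one SE shifts the estimate by (1−rho) × σ × sqrt(2/71), with σ set so that SD(A − B) = 18. The largest value is for exchangeable visits at rho = 0.5: σ = 18/sqrt(0.625) = 22.77, and 0.5 × 22.77 × 0.1678 = 1.91 points. The smallest is for perfectly correlated visits at rho = 0.8: σ = 18/sqrt(0.4) = 28.46, and 0.2 × 28.46 × 0.1678 = 0.96 points.

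**Does ppFEV1 already absorb the gain?** If it correlates equally with baseline and follow-up CFQ-R (0 to 0.5), no. If its link to follow-up runs only through baseline CFQ-R, it absorbs a little. With exchangeable visits, rho = 0.8 and a ppFEV1 correlation of 0.5, ppFEV1 alone brings the SD to 17.64 and both terms bring it to 16.50. The variance cut from adding CFQ-R is then 12.5% rather than 16%.

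**Validity by simulation** (ppFEV1 in both models at an assumed correlation of 0.35; 3,000 replicates per setting; rho 0.5 and 0.8; visit-to-visit correlation rho or 0.98). Type I error was 4.7% to 5.4% without baseline CFQ-R and 4.6% to 5.3% with it. Mean estimates were 9.99 to 10.08 for a true 10. Power was 90.8% to 91.2% without the term and 94.1% to 99.3% with it.

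**The case against.** The strongest reply is that nothing planned is broken. The covariates mirror the stratification, protocol 9.3.1 gives the reasons for those factors, and the sample size rests on an unadjusted t-test. No stated property depends on baseline adjustment. All of that stands, and it is why this is an efficiency point and not an error.

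The second reply is that the size of the gain is not a fact about this trial. That also stands. It depends on rho and on k, the ratio of follow-up SD to baseline SD. With perfectly correlated follow-up visits, the ratio is k²(1−rho²)/(k²+1−2k·rho). At k = 1.2 and rho = 0.8 that is 0.5184/0.52, a cut of only 0.3% (power 90.9%). At k = 1.1 and rho = 0.8 the cut is 3.2% (power 91.6%). With equal variances and rho = 0.9 it is 5% (power 92.1%). The gain vanishes when k × rho = 1. It also runs the other way: at k = 0.9 the cut is 25% at rho = 0.7, and it reaches about 50% with exchangeable visits and rho = 0.5. The 10% to 40% range therefore belongs to its assumptions and is not a floor and ceiling. The downside of adding the term is one degree of freedom in every case.

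On sweat chloride, protocol 12.3.3.3 calls for a model similar to the primary one rather than the same one, so substituting the endpoint's own baseline may have been intended. SwCl also lies outside the testing hierarchy and has only a nominal P value. This part is a request for clearer wording.

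**Conclusion.** The point holds as a precision loss in a valid analysis and is worth fixing. The omission is certain from the text; its cost is not. With rho between 0.5 and 0.8, equal variances and an SD of 18, the variance of the primary estimate is 10% to 40% lower with baseline CFQ-R. The planned precision would then be reached with about 43 to 64 completers per arm instead of 71. If follow-up scores are more variable than baseline scores, the gain could be close to nothing; if less variable, it could exceed the range. No SwCl gain can be computed from the documents.

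**What to change.** Before database lock and treatment unblinding, add continuous baseline CFQ-R respiratory domain score to the model in SAP 9.3.1.2 and to the subgroup models in 9.3.1.3, keeping baseline ppFEV1, age group and modulator use. A single main effect is enough; a baseline-by-visit term is optional, and the SAP should say which is used. In 9.3.3.2, state that the SwCl model includes continuous baseline SwCl, and whether baseline ppFEV1 stays alongside it.

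SAP section 4 already provides the route: "Any revisions to the approved SAP will be documented and approved in a SAP amendment prior to the clinical database lock". The cost is one model term and one degree of freedom. No data are added, and no subject is lost, because anyone with a change score has a baseline. Sample size and testing order are unchanged. The timing matters: a covariate added to the primary model after unblinding could look chosen on the result.

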9.3.1.3 Subgroup Analysis

Subgroup analyses of the primary efficacy endpoint will be performed using a model similar to that of the primary analysis for each of the following subgroups:

- Age at Screening (<18, ≥18 years)
- ppFEV₁ at Baseline (< 70, ≥ 70)
- CFTR modulator use at Screening (yes, no)
- Sex (male, female)

The MMRM used for the primary analysis will be used for the subgroup analysis, where the same model will be applied to each category of the subgroup. For the subgroup analysis based on age, the covariate of age at screening (<18 versus ≥18 years) from the MMRM will be removed. For the subgroup analysis based on CFTR modulator use at Screening, the covariate of CFTR modulator use at Screening (yes, no) from the MMRM will be removed. The LS means with 2-sided 95% confidence intervals will be provided. Furthermore, the estimated treatment difference through Week 24 in different categories within a subgroup will also be presented in a forest plot. Note that the results from the subgroup analysis should be interpreted with caution in the cases where sample sizes are small.

9.3.2 Analysis of Key Secondary Variable

9.3.2.1 Definition of Variable

The key secondary efficacy variable is the absolute change in ppFEV₁ from baseline through Week 24.

Percent predicted FEV₁ is the ratio of FEV₁ (L) to the predicted FEV₁ (L), expressed as a percentage. The predicted FEV₁ will be calculated using the Global Lung Function Initiative¹ (GLI); details are in [Appendix C](#).

9.3.2.2 Analysis Method

Analysis of this variable will be based on an MMRM that is the same as the primary efficacy variable, using the spirometry data obtained at clinic only. The primary result obtained from the model will be the estimated treatment difference through Week 24 (defined as the average of Weeks 4, 8, 16, 24). Data obtained from the Day 15, Week 4, Week 8, Week 16, and Week 24 Visits will be included in the model. The Day 15 Visit will not be included in the estimation of the average treatment effect through Week 24. The least squares (LS) mean estimate with a 2-sided 95% CI and a 2-sided P value will be provided. The treatment difference at each post-baseline visit, obtained from the model, will also be provided.

The LS mean (with SE) obtained from the MMRM analysis at each post-baseline visit up to Week 24 will be plotted by treatment group. In addition, the post-baseline raw values and the absolute change from baseline at each post-baseline visit up to Week 24 will be summarized descriptively (n, mean, SD, median, minimum, and maximum).

An additional analysis may be performed to include all available spirometry data obtained at clinic and obtained at home, if the spirometry data obtained at home are assessed to be reasonably consistent with the spirometry data obtained at clinic.

9.3.2.3 Multiplicity Adjustment

A hierarchical fixed-sequence testing procedure will be used to first test the primary endpoint and then test the key secondary endpoint, in order to control the overall family-wise type I error at a 2-sided alpha of 0.05. The key secondary endpoint (ppFEV₁) will only be tested if the primary endpoint is statistically significant.

9.3.3 Analysis of Secondary Variable

9.3.3.1 Definition of Variable

Sweat chloride (SwCl): the SwCl value for a given visit will be calculated as the mean of the non-missing sweat chloride measurements obtained on the left and right arms at that visit. If one of the two arm measurements at a time point is missing, the other will be used as the mean. A volume ≥ 15 μL is required for an accurate determination of sweat chloride. Any results reported as having volume < 15 μL will be considered missing. Any sweat chloride values reported as < 10 mmol/L or > 160 mmol/L will be considered missing.

9.3.3.2 Analysis Method

Analysis of absolute change from baseline through Week 24 in sweat chloride will be based on an MMRM that is same as the primary analysis of the primary efficacy variable. The primary result obtained from the model will be the estimated treatment difference through Week 24 (defined as the average of Weeks 4, 8, 24). The LS mean estimate with a 2-sided 95% CI and a 2-sided nominal *P* value will be provided. The treatment difference at each post-baseline visit, obtained from the model, will also be provided.

The LS mean (SE) at each visit will also be plotted by treatment group. In addition, the post-baseline raw values and the absolute change from baseline at each post-baseline visit up to Week 24 will be summarized descriptively (n, mean, SD, median, minimum, and maximum).

